Retroperitoneal bleeding		Clinical exam pre, during and immediately post alteplase infusion; every 6 hours post alteplase infusion up to 24 hours; at least every 24 hours after alteplase infusion during heparin infusion or more frequently if any abnormality detected. Endoscopic exam per attending's discretion.	Hemoglobin reduction $>3\text{g/dL}$ within 24 hours of infusion of study drug infusion or requiring RBC transfusion
Tube thoracotomy	Clinical exam and Hgb	Clinical exam pre, during and immediately post alteplase infusion; every 6 hours post alteplase infusion up to 24 hours; at least every 24 hours after alteplase infusion during heparin infusion or more frequently if any abnormality detected.	Hemoglobin reduction $>3\text{g/dL}$ within 24 hours of infusion of study drug infusion or requiring RBC transfusion
Any of the below listed exclusion criteria developing during or up to 3 hours after alteplase or heparin infusion. **	Clinical exam and laboratory		Any of listed exclusion criteria developing during or up to 3 hours after alteplase or heparin infusion.

*criteria or attending's decision

** criteria: Acute myocardial infarction; Acute Renal failure requiring dialysis; Liver failure (escalating liver failure with total Bilirubin $> 3 \text{ mg/dL}$); Cardiac tamponade; Bacterial endocarditis; Severe

uncontrolled hypertension defined as SBP>185mmHg or DBP>110mmHg; Seizure; Placement on ECMO; Major surgery required; Requirement of lumbar puncture; INR > 1.7; Platelet count < 100 x 10⁹/L or history of HIT.

Reporting of adverse events:

Any adverse event will be immediately and properly reported to IRB and DSMB, FDA and funding agency for discussion and feedback per regulatory guidelines.

Major Milestones, Tasks, Timelines and Deliverables

	Done	Essential For Initiation	Week From Secured Funding								Week 16
			1	2	3	4	5	6	7	8	
PREPARATION											
Establish Core Research Team	X										
Review existing literature	X										
Implement Protocol	X										
Finalize Study Protocol	X										
Finalize Statistical Analysis Plan	X										
Finalize Case Report Form	X										
Enlist Collaborating Institutions	X										
Submit Protocol for Funding	X										
Review Protocol Data	X										
REGULATORY OVERSIGHT											
FDA IND		X									
IRB Approval		X									
ClinicalTrial.gov Registration		X									
FUNDING SECURED											
Secure DSMB			X								
Hire Research Team	X										

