Study Protocol

v. 11/30/2020

Regulatory Sponsor: [name]

[name] Shock Trauma Center at Denver Health Medical Center

[name]

[name]

[contact]

Email: [contact]

Funding Sponsor: Genentech, Inc.

[name]

[name]

Study Product: Alteplase (Activase®)

Protocol title: Fibrinolytic Therapy to treat ARDS in the Setting of COVID-19 Infection: A Phase 2a Clinical Trial (former name "STudy of Alteplase for Respiratory failure in SARS-Cov2 (COVID-19): A Phase 2a Clinical Trial

NCT#: 04357730

IND#: 149634

COMIRB Protocol

COLORADO MULTIPLE INSTITUTIONAL REVIEW BOARD
[name] [contact] [contact]

Protocol #: 20-0880

Project Title: Fibrinolytic Therapy to Treat ARDS in the Setting of COVID-19 Infection: A Phase 2a Clinical Trial

Principal Investigator: [name]

Version Date: 11/30/2020

Abstract:

The global pandemic COVID-19 has overwhelmed the medical capacity to accommodate a large surge of patients with acute respiratory distress syndrome (ARDS).¹ In the United States, the number of cases of COVID-19 ARDS is projected to exceed the number of available ventilators¹. Reports from China and Italy indicate that 22-64% of critically ill COVID-19 patients with ARDS will die²⁻⁴. ARDS currently has no evidence-based treatments other than low tidal ventilation to limit mechanical stress on the lung⁵ and prone positioning⁶. A new therapeutic approach capable of rapidly treating and attenuating ARDS secondary to COVID-19 is urgently needed.

The dominant pathologic feature of viral-induced ARDS is fibrin accumulation in the microvasculature and airspaces. Substantial preclinical work suggests antifibrinolytic therapy attenuates infection provoked ARDS. In 2001, a phase I trial⁷ demonstrated the urokinase and streptokinase were effective in patients with terminal ARDS, markedly improving oxygen delivery and reducing an expected mortality in that specific patient cohort from 100% to 70%. A more contemporary approach to thrombolytic therapy is tissue plasminogen activator (tPA) due to its higher efficacy of clot lysis with comparable bleeding risk⁸. We therefore propose a phase IIa clinical trial with two intravenous (IV) tPA treatment arms and a control arm to test the efficacy and safety of IV tPA in improving respiratory function and oxygenation, and consequently, successful extubation, duration of mechanical ventilation and survival.

Rationale:

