- INR > 1.7 (with or without concurrent use of warfarin)
- Platelet count < 100 x 10⁹/L or history of HITT
- Fibrinogen < 300mg/dL
- Known abdominal or thoracic aneurysm
- History of CNS malignancy or CNS metastasis within past 5 years
- History of non-CNS malignancy within the past 5 years that commonly metastasizes to the brain (lung, breast, melanoma)
- Prisoner status

Patients will be sequentially assigned to one the following three groups as follows:

1. Group tPA50 will receive 50 mg of tPA intravenous bolus administration over 2 hours, given as a 10 mg push followed by the remaining 40 mgs over a total time of 2 hrs (not to exceed 0.9mg/kg dose). Immediately following the tPA infusion, 5000 U of UFH will be delivered and the heparin drip will be continued to maintain the activated partial thromboplastin time at 60-80sec (2.0 to 2.5 times the upper limit of normal). This tPA protocol is a modification of the GUSTO I to III trials.^{45,46}

2. Group tPA50 plus drip will receive 50 mg of tPA intravenous bolus administration over 2 hours, given as a 10 mg push followed by the remaining 40 mgs over a total time of 2 hrs (not to exceed 0.9mg/kg dose). Immediately following this initial tPA infusion, we will initiate a drip of 2 mg/hr tPA over the ensuing 24 hours (total 48 mg infusion) accompanied by an infusion of 500U/hour heparin during the tPA drip. After this, heparin dose will be increased slowly to maintain a PTT between 60 and 80 sec, titrated per attending's discretion.⁴⁷

3. Control: standard of care according to the institution's protocol for ARDS

Amendment Nov 4, 2020: please see below description for more detailed information on adaptation. The rationale for adjusting the tPA administration to a 50 mg bolus followed by a 2mg/hr infusion over the ensuing 24 hr is based on the facts that:

- 1) a convincing improvement in P/F was observed at 24 hr, but was lost over the ensuing 24 hr,
- 2) there was no discernable response to the second tPA bolus at the 24 hr time point,
- 3) we believe the initial 50 mg bolus has provoked fibrinolysis shutdown ;ie, PAI-1 generation in response to the tPA bolus blunting a response to a second bolus at 24 hr,
- 4) an infusion of low dose tPA will consume the PAI-1 generated in response to the initial tPA bolus and provide an additional fibrinolytic intervention over the ensuing 24 hr,

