- 5) the bolus/infusion regimen was employed in the seminal 2001, Hardaway study⁷ demonstrating an improvement in oxygenation in patients with advanced ARDS,

6) the 2mg/ml tPA and 500 U heparin is the standard combination employed by interventional radiology for directed fibrinolysis (personal communication [name], Director of IR, UCSD), and

7) we are reticent to increase the tPA dose to 100 mg considering overall risk: benefit.

The above modification was predicted in the original COMIRB submission, in which we anticipated both dose and mode of administration changes is our adaptive plan.

The rationale and change to a bolus/infusion regimen was discussed with the DSMB, and they concurred without reservation (see letter from DSMB, in which they concur with proposed plan).

[figure not shown]
Design:

This is a multicenter ([name] Shock Trauma Center at Denver Health Medical Center (DHMC), University of Colorado Hospital (UCH), National Jewish Health / St. Joseph Hospital (NJH/SJH), Beth Israel Deaconess Medical Center (BIDMC), Long Island Jewish Hospital / North Shore University Hospital (LIJH/NSUH), Scripps Health (SH), St. Mary's Medical Center (SM), University of Miami (UM), Ben-Taub General Hospital (BT) and Dallas Methodist (DM)) Phase IIa clinical trial. The design is a pragmatic, open label, randomized, controlled, rapidly adaptive clinical trial, with 3 interim analyses and 1 final look at the data. For rapid efficacy assessment to isolate the arm(s) with the highest likelihood of success and lowest bleeding risk, we will deploy each intervention arm sequentially up to each interim analysis, in a modified stepped-wedge fashion, with pre-planned adaptations (below) at each interim analysis. Pre-planned adaptations described below will be contemplated at each interim analysis or earlier if recommended by the Data Safety Monitoring Board (DSMB).

[figure not shown]

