All randomizations are conducted intra-hospital (i.e., no cluster randomization), to avoid the confounding effect of practice variation. Randomization will be conducted in blocks of 10 to allow better distribution between groups at each interim analysis. It will be done by the Data Coordinating Center (DCC) and automated in an web-based REDCap data collection instrument. Upon confirmed eligibility and consent, the REDCap will reveal the group assignment to institution's pharmacy, which will then release the drug if the patient is assigned to the intervention group (Group tPA50, Group tPA50+drip). Time zero is assigned as the time of randomization. We anticipate that each of the five centers will enroll 8-12 patients.

The figure below illustrates the initial planned sequential, stepped-wedge design and the proposed new design after the adaptations driven by the first interim analysis. Study will continue during the interim analyses, unless a safety issue occurs.

INITIAL DESIGN

NEW DESIGN AFTER 1st INTERIM ANALYSIS

Re-bolusing of tPA, at the same dose, is permitted in the tPA50 intervention group in those patients who show an initial transient response (>20% improvement of PaO₂/FiO₂ over pre-infusion of alteplase at any of the measurements at 2, 6, 12 or 18 hours, but <50% improvement of PaO₂/FiO₂ at 24 hours after randomization); the repeat dose will be given between 24 and 36 hours after the initial tPA administration.

The same EXCLUSION criteria apply to the second tPA (alteplase) bolus. The heparin drip should be stopped two hours before the second tPA (alteplase) and re-started after the second alteplase infusion ends, at the same dose as before the second alteplase.

Other modifications of the dosing are as follows:

- Fibrinogen monitoring:** For all tPA administration groups, fibrinogen levels will be measured before and after tPA IV bolus, 6 hours after the start of the infusion, then every 6 hours for first 24 hours, and once a day for 6 days following treatment intervention in all the groups (see detailed lab testing schedule below). **If fibrinogen levels fall below 300 mg/dL, the second bolus of tPA (alteplase) is NOT indicated.**

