There will be no adjustment for multiple outcomes, as all were pre-planned. The investigator-statistician in charge ([name]) strongly agrees with the argument that adjustment for multiple comparisons in pre-planned hypotheses leads to more type II errors.^{50,51}

Data Storage:

Data will be captured in the University of Colorado web-based REDCap instrument. The data collection form is in production in REDCap.

Criteria for cessation of administering drugs and safety assessments:

The estimated risk of intracranial hemorrhage is 0.72% ⁴⁵ if total tPA dose is < 1.4 mg/kg over total infusion. Estimated risk of severe or life-threatening bleeding other than intracranial is 0.4% ⁴⁵ if total tPA dose is <1.4mg/kg over total infusion. Per FDA guidelines will deliver bolus over 2 hours.

Specification of Safety Variables

Safety assessments will consist of monitoring and reporting adverse events (AEs) and serious adverse events (SAEs) per protocol. This includes any AE, defined as **any unfavorable and unintended sign (including an abnormal laboratory finding), symptom, or disease temporally associated with the use of an investigational medicinal product (IMP) or other protocol-imposed intervention, regardless of attribution.**

This protocol is limited to infusion of two IMPs, alteplase and heparin and blood sampling; thus given their relative short half-life of infusion drugs alteplase (<72 minutes) and heparin (<90 minutes), any effect listed below manifesting within 3 hours of administration of the intervention drugs would be considered potentially temporally related to the intervention drugs. Adverse events associated with blood sampling are considered temporally related if happening within 30 minutes of the sampling.

Safety check assessments: methods and timing

Serious adverse events and frequency of safety checks are as follows:

Serious Adverse Events	Method for safety check	Safety check frequency	Cessation rule *
Death	NA	NA	NA
Cardio-pulmonary arrest	NA	NA	Any cardio-pulmonary arrest
Allergic reactions including angioedema	Clinical exam	Clinical exam pre, during and immediately post alteplase infusion; every 6 hours post alteplase infusion up to 24 hours; at least every 24 hours after alteplase infusion during heparin infusion or more frequently if any abnormality detected.	Any allergic reaction

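### Bedside bleeding checks are scheduled only around study drug, so control bleeds may be under-ascertained and the tPA excess over control overstated

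*Protocol*

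**What the plan says.** **Aims.** The Protocol abstract proposes two tPA arms and a control arm "to test the efficacy and safety of IV tPA in improving respiratory function and oxygenation". The Design section deploys the intervention arms in sequence so as to "isolate the arm(s) with the highest likelihood of success and lowest bleeding risk".

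**Use of safety data.** Under Adaptive design (Protocol; SAP 3.4), an arm may be eliminated for adverse events judged attributable to the intervention by the trial team with the DSMB and IRB. The trial may stop if the DSMB finds the harm profile unacceptable (SAP 3.3).

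**Outcomes.** Neither list (Protocol, Outcomes; SAP 2.2) includes bleeding. The nearest item, coagulation-related arterial and venous event-free days, reads as thrombotic. SAP 6.4 mentions thrombotic complications but not bleeding. SAP 4.3 commits safety analyses to intention-to-treat and then as-treated, without naming a bleeding variable or comparison.

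**Ascertainment.** In the safety tables (Protocol, Criteria for cessation; SAP 7), every bleeding row that has an examination frequency times it before, during and after alteplase, six-hourly to 24 hours after the infusion, then at least daily while the heparin runs. The hemoglobin-fall criterion is also timed from study drug. An adverse event is defined by its timing relative to an investigational product or another protocol-imposed intervention.

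**What controls do have.** Laboratory tests, including CBC, follow one schedule in all groups to hour 168. Any adverse event is to be reported. For every patient, "Time zero is assigned as the time of randomization".

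**The concern.** A comparison of bleeding between a treated and an untreated group is fair only if both are examined equally often. Here the schedule begins with an infusion that controls never receive. The control group is not free of bleeding risk, because the Protocol's Heparin dosing section calls intravenous heparin standard of care for COVID-19 patients in the ICU. It does not say whether that heparin triggers the scheduled checks.

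In an open-label trial, staff who know that a patient received a fibrinolytic are likely to look harder as well. Both mechanisms push the same way: control bleeding is under-counted and the excess attributed to tPA looks larger than it is. At stake are the DSMB's view of harm at each remaining look, any decision to drop an arm for harm, and the safety estimate carried into the Phase III trial that the SAP says these results will inform.

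**Working it through.** The plan gives no figure for this point, so there is none to reproduce. The check is a comparison of capture by arm, followed by arithmetic for scale.

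**1. Scheduled capture, as written**

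| Type of bleed | tPA arms | Control |
|---|---|---|
| External, hemoptysis, hematuria | Examination timed from alteplase and the following heparin | No scheduled check |
| Neurological change | Same timing; imaging at the care team's discretion | No scheduled check; imaging not scheduled either |
| GI, retroperitoneal: clinical signs | Same timing | No scheduled check |
| GI, retroperitoneal: hemoglobin fall | CBC to hour 168 | CBC to hour 168 |
| Any adverse event reported spontaneously | Yes | Yes, but the definition is tied to a product or protocol-imposed intervention |

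The unequal part is bedside detection; the laboratory part is equal. I give no count of examinations per arm, because it depends on the infusion. With bolus plus drip, alteplase runs for 2 + 24 = 26 hours, so six-hourly checks counted from its end run to about hour 50.

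**2. Effect of one missed control bleed**

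Inputs: looks at 20, 30 and 50 patients (SAP 3.2, interim table) and 25 controls in total (SAP 3.2). I assume 1:1 allocation at each look. Shift in risk difference = 1 / number of controls.

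- Look 2, 10 controls: 1/10 = 10 points
- Look 3, 15 controls: 1/15 = 6.7 points
- Final, 25 controls: 1/25 = 4 points

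These are against all controls. Concurrent controls are fewer for each regimen, so each missed event would weigh more. Look 1 preceded this version and is left out.

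**3. Illustration of the average bias (assumed inputs)**

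Let r be the true bleeding risk in both arms and s the share of control bleeds captured. False excess = r(1 − s). Chance of at least one missed bleed in 25 controls = 1 − (1 − r(1 − s))^25.

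The documents give neither r for controls nor s. For a low value of r I borrow the Protocol's tPA risks for severe bleeding: 0.72% + 0.4% = 1.12%, assuming no overlap. These are not control risks. The 5% value is purely assumed.

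| r | s | False excess (points) | Chance of ≥1 missed |
|---|---|---|---|
| 1.12% | 75% | 0.28 | 6.8% |
| 1.12% | 50% | 0.56 | 13.1% |
| 1.12% | 25% | 0.84 | 19.0% |
| 5% | 75% | 1.25 | 27.0% |
| 5% | 50% | 2.5 | 46.9% |
| 5% | 25% | 3.75 | 61.5% |

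On these inputs the average bias is small. When a miss does happen, its effect is the shift in step 2.

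**4. Precision of a bleeding summary**

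Exact two-sided 95% upper limit with no events = 1 − 0.025^(1/n): 30.8% for 0/10, 21.8% for 0/15, 13.7% for 0/25.

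**The case against.** The strongest reply is that the tables exist to decide when to stop study drug. Controls have no study drug to stop, so timing from alteplase is natural, and nothing says these are the only means of finding a bleed. All patients are ventilated and closely nursed. Many of the listed bleeding criteria are hard to overlook: bleeding unresponsive to compression, hemoptysis or hematuria lasting four hours, or a transfusion. Any adverse event must be reported, CBC is equal across arms, and an intention-to-treat safety analysis implies some look by group. Overstating tPA harm is also the cautious direction.

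Most of this stands as mitigation. It does not make scheduled bedside detection equal, and reporting rules act only on what is found. Caution in one direction can still cost a useful arm.

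Four stronger readings are not supported:

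- **That control bleeds go unrecorded.** The documents do not say so. Blood sampling is protocol-imposed and applies to controls, and the three-hour window can be read as a rule for relatedness. Under-ascertainment is an inference.
- **That the choice of regimen is distorted.** The aim to "isolate the arm(s) with the highest likelihood of success and lowest bleeding risk" most naturally concerns the choice among tPA regimens. Both follow drug-timed checks, so missed control bleeds affect that choice less.
- **That a risk difference drives arm dropping.** The rule rests on attributed events and judgment. A background rate informs that judgment but is not a formal criterion.
- **That the dose condition on the quoted risks, "if total tPA dose is < 1.4 mg/kg over total infusion", is part of this problem.** It limits which patients those risks describe and has no bearing on ascertainment.

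**Conclusion.** The concern holds for the comparison of tPA with control. Followed as written, the plan schedules bedside bleeding checks on unequal terms in an open-label trial that names safety as something it tests. The likely direction is an overstated tPA excess, confined to clinically detected bleeds. The magnitude cannot be derived from the documents; it depends on an unknown control bleeding risk and an unknown capture rate. What can be stated is the leverage of one missed control bleed: 10, 6.7 and 4 points at looks 2, 3 and the end, given 1:1 allocation and comparison with all controls.

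The absent bleeding table alone would be a gap in detail. Together with unequal checks it merits a change, because equal capture is cheap and cannot be restored after the fact. Confidence is medium, since routine ICU care may already close much of the gap.

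**What to change.** **Protocol safety section and SAP 7.** Record bleeding in all arms from randomization, regardless of study-drug timing. Add one identical bedside bleeding check at the existing all-arm laboratory times (hours 6, 12, 18 and 24, then daily to hour 168), counted from randomization. Keep the drug-timed checks as an addition. Record heparin exposure in controls.

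**SAP 2.2 and 6.4.** Add a descriptive safety outcome, major bleeding, built from the SAP 7 criteria: new hemorrhage on imaging, external bleeding unresponsive to compression, persistent hemoptysis or hematuria, and GI or retroperitoneal bleeding. Count a hemoglobin fall above 3 g/dL in any 24 hours, or a transfusion, only when bleeding is suspected. At each remaining look and at the end, report counts by randomized arm with exact intervals, and a risk difference against concurrently randomized controls, intention-to-treat and then as-treated.

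**Cost.** A Protocol and SAP amendment, a short routine check in controls, and one table. Blood counts are already scheduled. Two limits remain. tPA patients still receive the extra drug-timed checks and staff still know the assignment, so the bias is reduced rather than abolished. The intervals will be wide (upper limit 13.7% even for 0/25), so the result is descriptive and cannot rank the arms formally.
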